3.5 Data collection methods

After providing written informed consent, patients commencing a new biologic treatment for their severe asthma will be asked to complete the SAQ (Appendix 2) and the EQ-5D-5L (Appendix 3) at the time of their first treatment. This is in addition to the Mini Asthma Quality of Life questionnaire (Mini-AQLQ) (Appendix 4) and Asthma Control Test (ACT) (Appendix 5) **or** Asthma Control Questionnaire (ACQ) (Appendix 6), which are normally completed as part of an appointment.

As this is a new biologic treatment, patients will be expected to attend a hospital appointment every 2 or every 4 weeks for subsequent treatments. The frequency of these visits is dependent on the biologic treatment that is prescribed.

In total there are five questionnaires. Participants will not be asked to complete all five at every visit. At 4, 8, 12 and 16 weeks participants will be asked to complete the Severe Asthma Questionnaire (SAQ) and the Global Rating of Change Questionnaire (GRCQ). At sixteen weeks participants will be asked to complete the EQ-5D-5L again in addition to the SAQ and GRCQ.

Once completed, the pseudonymised questionnaires will be scanned and sent to the Plymouth RA (JL) *via* NHSmail after each appointment.

Demographic Information and clinic data from week 0 (baseline) will be entered into the Baseline CRF (Appendix 9). Once completed, the Baseline CRF will then be scanned and sent to the Plymouth RA (JL) *via* NHSmail. Data collection from appointments at 0, 4, 8, 12 and 16 weeks will be entered into the Follow-up CRF (appendix 13). Once complete, the Follow-up CRF will be scanned and sent to the Plymouth RA (JL) *via* NHSmail.

Participant data from week 0 (baseline) will be added to the validation dataset. This will be explained to the patient on the Patient Information Leaflet (Appendix 12).

Copies of the questionnaires will also be placed in the patients' medical file at the participating site.

3.6 Analysis

The SAQ provides two scores, the SAQ score which is the mean of all 16 domain specific items, and the SAQ-global score which is a single item score based on the SAQ-Global, which itself is based on a Borg scale [21]. Borg scales use multiple quantifiers at empirically derived points along the scale with the aim of achieving a ratio scale. In this analysis plan, the term SAQ will refer to both the SAQ score and the SAQ global score. Separate analyses will be carried out on the SAQ score and SAQ-global. Several analyses will be carried to ensure that the MCID concept is fit for purpose.

Data from 4, 8, 12 and 16 weeks will be compared to the data collected at week 0 (baseline), providing 4 change scores per patient. Patients can indicate any one of 5 levels of improvement in any of the four weeks, or, if there is no change or deterioration, up to 11 types of change. If patients report the same level of global rating of change at each of the four time points (e.g., they record 'a little better' at week 4 and 'a little better at week 8), the average SAQ change score will be calculated for that patient. This average will then be used as the SAQ change for that particular level of global rating of change. This procedure is followed so that each patient can contribute just one value to the population average of the SAQ change score at any level of global change, and which, in the case of the level of 'a little better' is used to calculate the MCID. We shall carry out three analyses to check on the validity of the MCID concept. If the checks come out positive, then the existing method of calculating the MCID (i.e., as the change in the SAQ that maps on to the global rating of change criterion of 'a little better) will be adopted.

If the checks are negative – i.e., suggesting some revision to the way the MCID concept is employed – then we will adapt the methodology in accordance with our findings.

What degree of change on the SAQ is associated with each of the 5 levels of improvement and 5 levels of deterioration on the global rating of change score?

The mean, confidence intervals, and standard deviation of change of the SAQ will be calculated for each level of change in the GRCQ. These means will then be plotted (change in SAQ on x axis, global change on y axis) to show the relationship between change and perceived change at different degrees of change. These results should show that the change in the SAQ increases with increase in global change scores, and will be tested for by analysis of variance. This analysis is needed to show that the MCID is specific to the level of change of 'a little better' or 'a little worse' rather than any other level of global rating of change. The analysis will also check whether 'a little better' is equivalent in terms of 'a little worse' in terms of SAQ change.

Is the MCID transitive – i.e., is the MCID independent of level of deficit of quality of life?

Patients will be allocated to quartiles based on severity of the SAQ score at week 0. The mean, confidence intervals and standard deviation of change scores for change at 'a little better' will be calculated. Analysis of variance will be calculated for the four quartiles to test of transitivity. Effect size (eta) will be calculated. This analysis is needed to show that the MCID level can be applied across the full range of deficit of quality of life.

Are items in the SAQ equivalent with regard to the MCID – i.e., is change in all the 16 SAQ items equivalent in terms of their relationship with the global rating of change?

To test for equivalence, change in each of the 16 items of the SAQ and the SAQ-global will be correlated against the global rating of change score. These correlations will be examined and interpreted. Regression will be explored, but may be ruled out due to co-linearity. This analysis is needed to show whether weighting of items is needed when calculating the MCID, or whether the MCID is based simply on the mean of all items.

Demographic information analyses

In addition, we will also test whether baseline characteristics are similar across the four quartile groups and investigate whether the change in SAQ is related to the collected demographic and clinical data.

If the above show no problems with the existing methodology, then the MCID will be calculated from the average SAQ change for the rating of 'a little better'. That is, any patient who has provided a global rating of change of 'little better' will contribute an initial and final SAQ score to produce a SAQ difference score for each patient, and the average of the SAQ difference scores across patients will be then form the MCID. If there are problems, then we shall modify the MCID, for example, having different values for different levels of quality of life deficit (see 2 above) or by using a weighting of items (see 3 above).

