been increasing interest in identifying people at risk of asthma deaths, improving services for patients with severe asthma, and rational use of new treatments.

The SAQ questionnaire was derived from a qualitative study [8] and questions and design were evaluated by a panel of international expert clinicians. The concepts and wording were modified and tested in an iterative series of four focus groups of patients attending the difficult asthma service [9]. The questionnaire was then field tested in 160 patients and compared to the MiniAQLQ, the Asthma Control test and clinic data including BMI, lung function, and health care consumption [10]. The final version takes into account the lessons learned from this quantitative study and further input from the panel of experts.

The SAQ questionnaire has 16 questions rated on a 0-6 Likert scale and on a 0-100 scale rating of (i) overall quality of life (ii) how your asthma symptoms and the side effects of your medicines have affected your quality of life during the last two weeks.

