3.3 Study outcome measures

3.3.1 Investigation questionnaires:

1. Severe Asthma Questionnaire (SAQ) (Appendix 2)
2. Global Rating of Change Questionnaire (Appendix 10)

This scale will be used by participants to indicate how much better they feel since commencing a biologic treatment for asthma. The 11-point scale ranges from -5 (a great deal worse) to 5 (A great deal better) [20].
3. EQ-5D-5L (Appendix 3)

3.3.2 Clinic Data to be collected:

Baseline characteristics:

Age

Sex

Spirometry: absolute FEV1 (litres) and percentage of predicted FEV1 (FEV1 %)

Forced Vital Capacity (FVC) (litres)

Body Mass Index (BMI)

Asthma severity: Treatment level by drug class classified by GINA step
Maintenance OCS dose (mg/day)Health care utilisation:
Emergency Department attendance in the last 12 months
Hospital admissions in the last 12 months

Clinic Data Outcome Measures to be recorded at each treatment visit:

Weight (Kg)
Maintenance OCS dose (mg/day)
Number of exacerbations since last clinic visit requiring OCS Health care utilisation, the number of:
Emergency Department attendances since last clinic visit
Hospital admissions since last clinic visit.

Must be recorded on the follow-up CRF at the final study visit (16 weeks), (weeks 4, 8 and 12 are optional):

FEV1 (litres)
FEV1 (% predicted)

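### Section 3.6 averages SAQ change over weeks 4 to 16 within each rating level with no visit-week term, so a shared time trend could carry analysis 1 and shift the MCID

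*Protocol*

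**What the plan says.** Protocol section 3.5 sets the paired measurements: "At 4, 8, 12 and 16 weeks participants will be asked to complete the Severe Asthma Questionnaire (SAQ) and the Global Rating of Change Questionnaire". Section 3.6 compares each visit with week 0, "providing 4 change scores per patient". When a patient gives the same rating at more than one week, those SAQ changes are averaged: "This average will then be used as the SAQ change for that particular level of global rating of change".

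Analysis 1 is then defined by rating level alone: "The mean, confidence intervals, and standard deviation of change of the SAQ will be calculated for each level of change in the GRCQ". The expected result is that "change in the SAQ increases with increase in global change scores, and will be tested for by analysis of variance". If the three checks are positive, the mean change at 'a little better' is adopted as the MCID. The closing paragraph of section 3.6 describes that calculation differently. There each patient contributes a starting and an end SAQ score, and the visit that counts as the end is not named.

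The rating, per section 3.3, asks patients "how much better they feel since commencing a biologic treatment for asthma". Its reference point is fixed, so the recall period lengthens from 4 to 16 weeks. Section 1.1 describes the SAQ's 0-100 rating as covering how symptoms and side effects "have affected your quality of life during the last two weeks".

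Visit week is not a factor, stratum or covariate anywhere in section 3.6. The only further work on SAQ change uses demographic and clinical data.

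**The concern.** Every patient in this part of the study has just started a biologic, so SAQ change and the rating may both rise between week 4 and week 16. Low ratings such as 'a little better' would then come mainly from early visits and high ratings from late ones. Level means could rise with the rating even if, at any one visit, a patient's rating said little about that patient's SAQ change.

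Separately, the averaging rule treats 'a little better' over 4 weeks and over 16 weeks as the same quantity. Section 3.6 tests whether the MCID holds across baseline severity (analysis 2) and whether items behave alike (analysis 3), but has no check across time.

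At stake are the meaning of a positive analysis 1, which helps decide whether the MCID method is adopted, and whether one MCID suits both short and longer follow-up. A later analysis plan would not simply fill this in, because the averaging rule already written in the protocol discards the visit.

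**Working it through.** **Plan's own figure.** Section 3.4.3 states 70% power for four groups of 25 at effect size 0.3 and a 5% level. One-way analysis of variance, noncentrality f²N = 0.3² × 100 = 9, with 3 and 96 degrees of freedom, gives 69.2%. This agrees, but it concerns analysis 2 and does not bear on this point.

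**Inputs.** From the protocol: 100 patients, four visits, an 11-point rating (-5 to 5), one averaged value per patient per rating level, and analysis of variance across levels. Assumed, because the documents do not give them: the time trends, a rating SD of about 1.5 points, the within-patient correlation, and SAQ change in SD units.

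**Can a shared trend alone give a significant analysis 1?** The first setting has within-patient correlation 0.6 and no relation between SAQ change and rating within any visit. Ranges cover repeated simulations.

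| Mean SAQ change, week 4 to 16 | Mean rating, week 4 to 16 | Rating rise in SD | Significant |
|---|---|---|---|
| no trend | no trend | 0 | 3% |
| 0.30 to 0.75 SD | 1.0 to 2.5 | 1.5/1.5 = 1.0 | 6-9% |
| 0.25 to 0.95 SD | 0.75 to 2.9 | 2.15/1.5 = 1.43 | 29-30% |
| 0.20 to 1.10 SD | 0.5 to 3.2 | 2.7/1.5 = 1.8 | 63-66% |

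After removing visit means the share is 2-3%. In the strongest case, a random-intercept model gave a significant positive slope in 100% of runs without visit week and in about 5% with it.

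A second setting uses an equal rise in both measures and within-patient correlation 0.3 to 0.7.

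| Rise in both, week 4 to 16 | Significant |
|---|---|
| 0 | 2-4% |
| 0.5 SD | 3-5% |
| 0.8 SD | 15-17% |
| 1.0 SD | 30-36% |
| 1.5 SD | 91-96% |

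After centring by visit the share is 1-4% throughout.

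**If SAQ change and rating are related within a visit.** In the first setting with correlation 0.3, the planned test is significant in 95% of runs with no trend and 99-100% with the trends. With correlation 0.5 it is 100% throughout.

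**Does the 'a little better' mean depend on the visit?** For rating g at week w, with within-visit correlation r, the expected SAQ change in SD units is

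m(g, w) = SAQ mean(w) + r × (g − rating mean(w)) / rating SD.

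So the week 16 minus week 4 difference at a fixed rating is (SAQ rise) − r × (rating rise in SD).

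- r = 0, both rise 1.0 SD: difference 1.0. Simulated: about 0.3 at week 4, 1.3 at week 16, 0.73 pooled.
- r = 0.5, both rise 1.0 SD: 1.0 − 0.5 = 0.5. Simulated: 0.29, 0.80, 0.51 pooled.
- r = 0.3, strongest trend of the first setting: 0.90 − 0.3 × 1.8 = 0.36.
- r = 0.5, same trend: 0.90 − 0.5 × 1.8 = 0. Simulated: 0.36 at week 4, 0.40 at week 16.

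**How much data per visit?** In that strongest trend about 65% of 'a little better' ratings come from weeks 4 and 8. About 25 patients give that rating at week 4 and about 9 at week 16. The 95% half-width at week 16 is 2.31/√9 = 0.77 SD. For the difference it is 2.04 × √(1/25 + 1/9) = 0.79 SD.

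**The case against.** The high false-pass rates need two things together: almost no within-visit relation and a steep shared trend. The documents state neither. With an equal rise of 0.5 SD or less the test stays near its nominal level, and with a correlation of 0.3 it passes almost always without any trend. This stands and limits the point.

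A significant analysis of variance is also not the whole check. Section 3.6 expects change to increase with the rating and wants the means plotted with intervals. Requiring the means to rise at every step from rating 0 to 4 (one reading of that text) cut trend-only passes from 8%, 30% and 63% to 1%, 8% and 23%. This lowers the risk but does not remove it.

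A reader might infer that analysis 3 is satisfied by a common trend too. The text does not support this. It says "change in each of the 16 items of the SAQ and the SAQ-global will be correlated against the global rating of change score", without saying which visits enter. That analysis compares items with one another, and a trend shared by all items raises all the correlations together. No calculation here covers unequal item trends.

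Finally, some of the joint movement between visits may be real improvement that patients perceive and rate. A visit term removes it along with any artefact, so the adjusted result is not automatically the better one.

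None of this answers the plain gap that weeks are averaged with no visit term and no look across time.

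**Conclusion.** The point holds in limited form. Section 3.6 fixes an average over weeks 4 to 16 within each rating level and tests level differences without visit week, while the recall period of the rating grows fourfold. Two consequences are possible, and neither is shown to occur.

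- With little within-visit relation and a marked shared trend, analysis 1 can be significant through the trend alone: from 6-9% up to 63-66% of studies in the first setting, against 2-3% after visit centring. With a within-visit correlation of about 0.3 or more, the check passes regardless.
- The pooled MCID can depend on the visit mix. The week 4 to week 16 difference at 'a little better' ranged from about nil to 1.0 SD over the assumptions tried, and was 0.5 SD in one case with a real correlation of 0.5.

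A reader might conclude that the validity checks are broken or that the MCID will be wrong. The documents give no trend, SD or correlation from which to say so. Nor do they support calling a single MCID valid only if the visits agree. No margin is defined, and with about 9 ratings at week 16 the data could not show agreement.

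**What to change.** In section 3.6:

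1. For analysis 1, add a model of visit-level SAQ change on rating level plus visit week, with a patient random effect. Report it beside the planned analysis of variance, as a supplement and not a replacement.
2. Beside the pooled MCID, give a descriptive sensitivity table of the mean SAQ change at 'a little better', with confidence interval and number of patients, by visit week. State that the pooled value averages over 4 to 16 weeks.
3. Reconcile the averaging rule with the closing paragraph's starting and end scores. If the end score means week 16 only, the averaging rule does not apply to the MCID. If it does not, say how several visits form one score.

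No new data are needed, only protocol wording, one extra model and one table. The cost is wide by-visit intervals, especially at week 16, so the table should be read descriptively and a lack of significant difference should not be taken as agreement.

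### Analysis 1 cannot show that the global rating measures change since baseline, and the example response to a failed analysis 2 would turn an anchor fault into severity-specific MCIDs

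*Protocol*

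**What the plan says.** The anchor is an 11-point scale from -5 to 5. Section 3.3 describes it so: "This scale will be used by participants to indicate how much better they feel since commencing a biologic treatment for asthma". Section 3.5 fixes its timing: "At 4, 8, 12 and 16 weeks participants will be asked to complete the Severe Asthma Questionnaire (SAQ) and the Global Rating of Change Questionnaire". Section 3.6 defines the outcome: "Data from 4, 8, 12 and 16 weeks will be compared to the data collected at week 0 (baseline), providing 4 change scores per patient".

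Section 3.6 then sets up its checks: "We shall carry out three analyses to check on the validity of the MCID concept".

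- Analysis 1 compares SAQ change across GRCQ levels by ANOVA: "These results should show that the change in the SAQ increases with increase in global change scores, and will be tested for by analysis of" (the quote stops one word short).
- Analysis 2 takes SAQ change at *a little better* and splits patients by week-0 SAQ: "Analysis of variance will be calculated for the four quartiles to test of transitivity".
- Analysis 3 works at item level: "change in each of the 16 items of the SAQ and the SAQ-global will be correlated against the global rating of change score".

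The decision rule begins "If the checks come out positive, then the existing method of calculating the MCID" and says that this method will be adopted. If the checks are negative, section 3.6 promises to adapt the methodology. Its closing paragraph gives two examples: MCID values that vary with the level of quality-of-life deficit, or weighting of items. Neither example, and none of the three analyses, relates the rating to week-0 SAQ and follow-up SAQ separately.

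**The concern.** An anchor-based MCID means what it claims only if the rating reflects change since baseline. A patient asked how much better they feel may in practice report how they feel that day. Because SAQ change is follow-up minus baseline, such a rating shares the follow-up score with the outcome and will be associated with it. The null hypothesis of analysis 1 is that the rating is unrelated to SAQ change. Rejecting it does not show that the rating carries information about where the patient started.

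If the rating follows present state, the mean change at *a little better* is the distance from this cohort's baseline to a roughly fixed follow-up level. That distance depends on how ill the recruited patients were. Section 1.2 wants the MCID for clinical practice, clinical trials and research, so transfer to other cohorts matters.

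**Working it through.** **The plan's own figure.** Section 3.4.3 states 70% power for four groups of 25, effect size 0.3, 5% level. Reading 0.3 as Cohen's f, the noncentrality is 0.3² × 100 = 9, and the noncentral F gives 69.2%. The figure is reproduced and is not in dispute.

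**Inputs.** From the protocol: N = 100, GRCQ scored -5 to 5, rating and SAQ at the same visit, change measured from week 0. Assumed, because the protocol does not give them: equal SAQ SDs at both visits; correlation r between baseline (X0) and follow-up (X1) SAQ of 0.3 to 0.85; loading L of the rating (G) on whatever drives it, 0.7 to 0.9. Rating noise with SD 0.75 of the signal corresponds to L = 1/√(1 + 0.75²) = 0.8. One visit per patient is simulated; averaging a patient's repeated ratings does not remove the shared follow-up score.

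**Step 1: expected correlation for a state-only rating.** With SAQ SD 1, the covariance of G with X1 - X0 is L(1 - r), and the SD of X1 - X0 is √(2(1 - r)). Hence corr(G, X1 - X0) = L√((1 - r)/2), which is positive for every r below 1.

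**Step 2: how often analysis 1 is significant with a state-only rating** (nominal 5%; ranges are over repeated simulations).

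| r | correlation, L = 0.8 | ANOVA significant, noise SD about 0.75 |
|---|---|---|
| 0.3 | 0.8 × √0.35 = 0.47 | 95-97% |
| 0.5 | 0.8 × √0.25 = 0.40 | 80-86% |
| 0.7 | 0.8 × √0.15 = 0.31 | 50-54% |
| 0.8 | 0.8 × √0.10 = 0.25 | 31-36% |

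With L from 0.7 to 0.9 the ranges are 86-99% at r = 0.3, 66-92% at 0.5, 38-70% at 0.7 and 19-36% at 0.85. A true change rating is significant in 100% of runs throughout, so a pass does not separate the two kinds of rating.

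**Step 3: analysis 2.** Counting ratings +1 and +2 as *a little better* (an assumption), it rejects in 64-100% of runs with a state-only rating. With a valid but noisy change rating it rejects in 9-62%, and in most settings between about 10% and 50%. It is sensitive to the fault but not specific to it.

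**Step 4: the checks combined.** A state-only rating passes analysis 1 and escapes analysis 2 in 0.4-6% of studies if *a little better* covers two rating levels, and in 14-19% if it covers one. A further simulation gave about 0-14%.

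**Step 5: analysis 3.** With L = 0.8 and an assumed item loading of 0.75, a state-only rating gives a mean item correlation of 0.25 at r = 0.5 and 0.17 at r = 0.7; 70% and 38% of items reach p < 0.05.

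**Step 6: what separates the cases.** Regress G on X0 and X1 together. If G = L·X1 + noise, the X0 coefficient is 0 and the ratio (X0 to X1) is 0. If G is proportional to X1 - X0 plus noise, the ratio is -1. A rating giving half weight to baseline has ratio -0.5. In simulation the week-0 coefficient is significantly negative in about 4-7% of state-only studies and 100% of change-anchored studies.

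**Step 7: effect on the MCID in the extreme case.** If baseline is 0.5 SD worse and follow-up unchanged, the MCID grows by 0.48-0.50 SD with a state-only rating, against 0.05-0.19 SD with a change rating. If the cohort is 0.5 SD worse at both visits, the shift is 0.10-0.23 SD, against zero.

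**The case against.** A reader might infer that a current-state rating would pass the planned checks and be adopted. The protocol does not support that. Adoption rests on three analyses, and analysis 2 conditions on baseline; step 4 shows that few such ratings would get past both it and analysis 1.

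A reader might also infer that the protocol commits itself to severity-specific MCIDs when analysis 2 fails. It does not: they are given only as an example, beside a general promise to adapt the methodology, and questioning the anchor is not excluded.

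Nor should analysis 3 be called a test that rejects for the wrong reason. It has no rejection rule, and its stated purpose is to decide on item weighting. Analysis 1's stated purpose is specificity to *a little better* or *a little worse*. Still, section 3.6 presents all three as validity checks for the MCID.

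Nothing in the protocol suggests that the GRCQ in fact reflects present state alone; its question is about change since starting the biologic. The figures in steps 2 to 5 and 7 for a state-only rating describe the extreme, and partial dependence gives a smaller bias.

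Finally, an anchor diagnostic could be left to a statistical analysis plan. But the protocol itself fixes the checks, the adopt-if-positive rule and the example responses, so the point concerns what is stated, not what is left out.

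What stands is that analysis 1 cannot distinguish the two kinds of rating, that analysis 2 reacts to both, and that the example response to its failure assumes the anchor is sound.

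**Conclusion.** The point holds with limited scope. A significant analysis 1 is not evidence that the GRCQ measures change since baseline. How often a purely state-driven rating would pass it depends on a correlation that the protocol does not give: nearly always at 0.3, about half the time at 0.7, about a third at 0.8. Analysis 2 would usually raise a flag, but it cannot tell a faulty anchor from a valid noisy one or from an MCID that truly varies with deficit. Following the example in section 3.6 at that point would report an anchor problem as a set of severity-specific MCIDs. These conclusions assume equal SDs, one visit per patient and the stated range of rating noise; the analysis 2 figures also depend on which rating levels count as *a little better*. This is a worthwhile improvement to a stated method, not a defect that invalidates the study.

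**What to change.** Add to analysis 1, at each of weeks 4, 8, 12 and 16, a regression of the GRCQ on week-0 SAQ and same-visit SAQ together, run separately for the SAQ score and SAQ-global as section 3.6 already requires. Report both coefficients and their ratio with a confidence interval: about -1 indicates a change rating, about 0 a current-state rating. Do not set a hard cut-off on the ratio, since intermediate values such as -0.5 are plausible and should be reported as they are.

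State in section 3.6 that this regression is consulted before a failed analysis 2 is answered with severity-specific values. If the week-0 coefficient is not clearly opposite in sign to the follow-up coefficient, report that the rating appears to reflect current state, and present the *a little better* mean, overall or by severity, only with that caveat.

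The cost is one extra analysis on data already collected, with no added patient burden. The downside is that the MCID may have to carry a caveat.

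### Section 3.6 names analysis of variance for a directional and a specificity claim about the MCID, but an overall F test alone supports neither

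*Protocol*

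**What the plan says.** Section 3.6 plans three checks on the MCID concept, and they decide what follows: "If the checks come out positive, then the existing method of calculating the MCID" is adopted, and otherwise the method is adapted.

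The first check relates SAQ change to the 11-point global rating of change (GRCQ), which section 3.3.1 scores from -5 to 5. It has these parts:

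- Estimates by level: "The mean, confidence intervals, and standard deviation of change of the SAQ will be calculated for each level of change in the GRCQ".
- A plot: "These means will then be plotted (change in SAQ on x axis, global change on y axis) to show the relationship".
- A directional hypothesis with its test: "the change in the SAQ increases with increase in global change scores, and will be tested for by analysis of variance".
- A specificity purpose: "This analysis is needed to show that the MCID is specific to the level of change of 'a little better' or 'a little worse", as opposed to other rating levels.
- A symmetry comparison: "The analysis will also check whether 'a little better' is equivalent in terms of 'a little worse' in terms of SAQ change".

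Section 3.6 names no trend test, no comparison of *a little better* with its neighbouring levels, and no criterion for calling this check positive.

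**The concern.** The hypothesis is ordered and the specificity statement concerns particular levels. The overall F test of an analysis of variance asks only whether any level mean differs from any other. It does not use the order of the ratings, and it does not compare *a little better* with *no change* or with the next level up.

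The check helps decide whether the standard MCID is adopted. If a significant F were taken as a pass, the MCID could be presented as specific to *a little better* when larger rated improvements carry the same SAQ change. If a non-significant F were taken as a fail, a real graded relation could be missed, because the test spreads its power over as many as 10 degrees of freedom, some of them on sparse levels.

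**Working it through.** **The plan's own figure.** The only stated power is for the quartile analysis (section 3.4.3): four groups of 25, effect size 0.3, 5% level, 70% power. Reading 0.3 as Cohen's f, the noncentrality is N × f² = 100 × 0.09 = 9 on 3 and 96 df, which gives 69.2%. The figure is reproduced. No power is stated for the first check.

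**Order does not affect F.** Assume six levels, 17 patients per level, SD 1, and level means 0, 0.2, 0.4, 0.6, 0.8, 1.0.

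- F noncentrality = n × Σ(mean − grand mean)² = 17 × 0.70 = 11.9 on 5 df. It depends on the set of means and not on their order.
- Linear contrast with coefficients -2.5 to +2.5: Σc² = 17.5 and Σc × mean = 3.5. The t noncentrality is 3.5 / √(17.5/17) = 3.45, and 3.45² = 11.9. The same signal falls on 1 df.

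Rejection rates over 20,000 simulated data sets per pattern (F at 5%; trend in the rising direction at one-sided 2.5%):

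| True means | Overall F | Rising trend |
|---|---|---|
| Rising | 74% | 93% |
| Same means, shuffled | 74% | 0.3% |
| Same means, reversed | 74% | 0% |

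With means 0, 0.3, 0.3, 0.3, 0.9, 0.9, F rejects in 72%, although the second and third levels are identical. A direct contrast of those two rejects in 5%.

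**A rating distribution closer to the study.** These inputs are assumptions; the documents give none of them. One value per patient; probabilities for -5 to +5 of .01, .01, .02, .03, .05, .13, .15, .20, .20, .13, .07 (75% improved, rating SD 2.06). For N, section 3.4.3 gives 100, or 125 with a fifth site, while section 3.2 gives 30 to 50 at each of five sites, so 150 to 250. Both ranges are shown. Results are simulated, with ranges across repeat runs.

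| N | F, graded r = 0.30 | Trend, graded r = 0.30 |
|---|---|---|
| 100 | 48% to 51% | 86% |
| 125 | 61% to 63% | 92% to 93% |
| 150 | 71% to 72% | 96% to 97% |
| 250 | 94% to 95% | over 99% |

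At r = 0.40, F power is already 82% to 83% at N = 100 and about 97% at N = 150.

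**No specificity.** Let all five improvement levels share the same 0.8 SD change, with none elsewhere. F is significant in 59% to 61% of runs at N = 100 and 71% to 73% at N = 125. The trend test is significant in 74% to 76% and 83% to 85%. A trend therefore answers the question of increase but not that of specificity.

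**Precision of neighbouring differences.** Take *a little better* as +1 and the next level as +2 (an assumption, since section 3.3.1 labels only the end points). At r = 0.30 the true step is 0.30/2.06 = 0.146 SD, and the residual SD is √(1 − 0.09) = 0.954.

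- N = 100 (15 and 20 patients): SE = 0.954 × √(1/15 + 1/20) = 0.326; 95% half-width about 0.65 SD.
- N = 250 (37.5 and 50 expected): SE = 0.954 × √(1/37.5 + 1/50) = 0.206; half-width about 0.41 SD.

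Under a truly graded relation with r from 0.30 to 0.50, this difference is significant in only about 6% to 14% of runs at N = 100 and 11% to 27% at N = 250.

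**The case against.** **Analysis of variance can carry contrasts.** The text does not say that the test will be an unordered overall F. Polynomial or pairwise contrasts belong to the same method, and an analysis plan that is not shown may specify them. This stands. A reader might infer that the protocol commits to an overall F and would adopt the MCID on it alone; the text supports neither step. What remains is that section 3.6 itself attaches a directional claim to a test which, in its plain form, has no direction.

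**The descriptive outputs would reveal the problem.** Equal SAQ change at *a little better* and at higher levels would show in the planned means, intervals and plot. This also stands in part, so the first check does not rest on the F test alone. But nothing says how these outputs bear on whether the check is positive.

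**Other comparisons are planned.** Comparing *a little better* with *a little worse* addresses symmetry, not separation from neighbouring levels. The third analysis does use the rating as an ordered score: "change in each of the 16 items of the SAQ and the SAQ-global will be correlated against the global rating of change score". Its purpose is item weighting, and the 16-item mean score is not listed. These soften the gap without closing it.

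**The power loss is small in a larger study.** This is correct. A reader might infer that the check is underpowered, but at the 150 to 250 patients of section 3.2, or at r = 0.40, F mostly detects a graded relation. Section 3.6 also allows a patient to contribute one value at each level reported, up to four in all, so one value per patient is a simplification.

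**Conclusion.** The point holds in limited form. Section 3.6 names analysis of variance for an ordered hypothesis, within an analysis also meant to establish specificity, and an overall F test alone supports neither. That conclusion follows from how F is built and needs no assumed inputs.

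The power cost does depend on assumptions. At a graded correlation of 0.30 it is about 50% against 86% at N = 100, and 71% to 95% against at least 96% at N = 150 to 250. It is small at higher correlation or N.

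Severity is minor to moderate. The sample size rests on the quartile analysis, so no stated number changes. The MCID estimate, the mean SAQ change at *a little better*, does not use this test. What is affected is the basis for calling the first check positive.

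One might also conclude that significance tests between neighbouring levels should replace F as the pass or fail rule. The precision figures argue against this: such a rule would usually fail even when SAQ change truly rises with the rating.

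**What to change.** Amend the first analysis in section 3.6 as follows:

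1. Test the increase by the linear trend of SAQ change on the GRCQ scored -5 to +5, and state that a significant overall F does not count as a positive check.
2. Judge specificity from the planned level means. Report, with 95% confidence intervals, the difference between *a little better* and *no change* and the difference between *a little better* and the next level up. Treat both as estimates and not as a significance gate. Where the intervals do not separate the levels, state that specificity was not shown.

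The cost is a few sentences; the data and sample size are unchanged. The drawback is that the two differences will usually be imprecise at the planned size, so the conclusion on specificity will often be weak.
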